	Grade 2 or 3	
 • Withhold study treatment. • Investigate etiology. Consult with a gastroenterologist if immune etiology is suspected. • Treat immune diarrhea/colitis with corticosteroids following guidance provided in the Appendix 10. • If diarrhea improves to Grade ≤ 1, resume obinutuzumab at full dose and resume lenalidomide at a reduced dose ^a per guidelines in Section 5.1.5. In case of immune-mediated event, atezolizumab may be resumed at full dose if colitis has cleared as confirmed by sigmoidoscopy (or colonoscopy, if appropriate) with colonic biopsy. Discuss with Medical Monitor before resuming atezolizumab. 
Note: If colitis is treated with corticosteroids, atezolizumab should not be resumed until the corticosteroids have been tapered to ≤ 10 mg/day of prednisone or equivalent (refer to Appendix 10 for guidance).

Table 11 Guidelines for Management of Non-Hematologic Toxicities (cont.)

Event		Action to Be Taken
Pneumopathy, non-infectious (i.e., dyspnea, hypoxia, pulmonary infiltrates)	Grade 3 or 4	
 • Permanently discontinue atezolizumab. Withhold obinutuzumab and lenalidomide. • Investigate etiology. Consult with a pulmonologist if immune etiology is suspected (refer to Appendix 10 for guidance). • Treat immune-mediated pneumopathy with corticosteroids following guidance provided in the Appendix 10. • If symptoms have resolved and CT lung findings are clear, resume obinutuzumab at full dose and resume lenalidomide at current dose.
	Grade 2	
 • Withhold atezolizumab for immune-mediated pneumopathy. • Treat with corticosteroids following guidance provided in the Appendix 10. • If there is improvement to Grade ≤ 1, resume atezolizumab after corticosteroids have been tapered (refer to Appendix 10 for guidance). Discuss with Medical Monitor before resuming atezolizumab. • Treat as Grade 3–4 if recurrent episode of immune pneumopathy.
Tumor flare reaction	Grade 3–4 ^c	
 • Withhold study treatment. • Administer corticosteroids, NSAIDs, and/or narcotic analgesics at investigator's discretion. • If there is improvement to Grade ≤ 1, resume obinutuzumab and atezolizumab at full dose and resume lenalidomide at a reduced dose per guidelines in Section 5.1.5 for current and subsequent cycles.
	Grade 1–2 ^c	
 • Continue study treatment. • Administer corticosteroids, NSAIDs, and/or narcotic analgesics at investigator's discretion.

Table 11 Guidelines for Management of Non-Hematologic Toxicities (cont.)

Event		Action to Be Taken
Dermatologic toxicity: Grade ≥ 2	Grade 3 with blistering or Grade 4	
 Permanently discontinue study treatment.
	Grade 2 or Grade 3 without blistering	
First occurrence:
 
 Withhold study treatment and evaluate patient at least every 7 days. Investigate etiology. Consult with a dermatologist. Topical corticosteroids may be required. If immune etiology is suspected, consider oral prednisone 10 mg or equivalent. If event is unresolved after 48–72 hours, administer oral prednisone 60 mg or equivalent. If there is improvement to Grade ≤ 1, resume obinutuzumab at full dose and resume lenalidomide at a reduced dose^a per guidelines in Section 5.1.5 for current and subsequent cycles. Atezolizumab may be resumed at full dose if the event is resolved and systemic corticosteroids dose is ≤ 10 mg/day of oral prednisone or equivalent. Contact Medical Monitor before resuming atezolizumab. 
Second occurrence:
 
 Permanently discontinue study treatment.
Hypothyroidism		
 Investigate etiology. Consult with an endocrinologist (refer to the Appendix 10 for guidance if immune etiology is suspected). Start thyroid replacement hormone. Monitor TSH weekly. 
Asymptomatic elevation of TSH
 
 Continue study treatment. 
Symptomatic elevation of TSH
 
 Withhold study treatment. If symptoms are controlled and TSH levels are decreasing, resume obinutuzumab and atezolizumab at full dose and lenalidomide at current dose. Permanently discontinue atezolizumab for Grade ≥ 3 hypothyroidism.

Table 11 Guidelines for Management of Non-Hematologic Toxicities (cont.)

Event	Action to Be Taken
Hyperthyroidism (cont.)	
For asymptomatic patients with TSH < 0.5 mU/L:
 
 • Perform TSH, free T4, and T3 tests every 4 weeks. 
For asymptomatic patients with TSH < 0.1 mU/L or symptomatic patients:
 
 • Withhold study treatment. • Consider consultation with an endocrinologist. • Administer methimazole as needed. • Resume atezolizumab when symptoms are controlled by thyroid hormone replacement. • Permanently discontinue atezolizumab for life-threatening hyperthyroidism.
Hypophysitis (pan-hypopituitarism)	Grade 4 
 • Permanently discontinue atezolizumab and contact Medical Monitor. • Refer patient to endocrinologist. • Perform brain MRI (pituitary protocol). • Initiate treatment with 1–2 mg/kg/day IV methylprednisolone or equivalent and convert to 1–2 mg/kg/day oral prednisone or equivalent upon improvement. • Initiate hormone replacement if clinically indicated.
	Grade 2 or 3 
 • Withhold atezolizumab. • Refer patient to endocrinologist. • Perform brain MRI (pituitary protocol). • Initiate treatment with 1–2 mg/kg/day IV methylprednisolone or equivalent and convert to 1–2 mg/kg/day oral prednisone or equivalent upon improvement. • Initiate hormone replacement if clinically indicated. • Resume atezolizumab if event resolves to Grade 1 or better, and patient is stable on replacement therapy (if required) within 12 weeks. • If event does not resolve to Grade 1 or better while withholding atezolizumab, permanently discontinue atezolizumab and contact Medical Monitor. • For recurrent hypophysitis, treat as a Grade 4 event.

Table 11 Guidelines for Management of Non-Hematologic Toxicities (cont.)

Event		Action to Be Taken
Hyperglycemia	Grade 3–4	
 • Withhold atezolizumab. • Initiate treatment with insulin. • Monitor for glucose control. • Resume atezolizumab when symptoms resolve and glucose levels are stable.
	Grade 1 or 2	
 • Continue atezolizumab. • Investigate for diabetes. If patient has Type 1 diabetes, treat as a Grade 3 event. If patient does not have Type 1 diabetes, treat as per institutional guidelines. • Monitor for glucose control.
Symptomatic adrenal insufficiency	Grade 2–4	
 • Withhold atezolizumab. • Refer patient to endocrinologist. • Perform appropriate imaging. • Initiate treatment with 1–2 mg/kg/day IV methylprednisolone or equivalent and convert to 1–2 mg/kg/day oral prednisone or equivalent upon improvement. • Resume atezolizumab if event resolves to Grade ≤1 and patient is stable on replacement therapy (if required) within 12 weeks. If corticosteroids have been initiated, they must be tapered over ≥ 1 month to ≤ 10 mg/day oral prednisone or equivalent before atezolizumab can be resumed. Contact Medical Monitor before resuming atezolizumab.
Immune-mediated myocarditis	Grade 3–4	
 • Permanently discontinue study treatment and contact Medical Monitor. • Refer patient to cardiologist. • Initiate treatment as per institutional guidelines and consider antiarrhythmic drugs, temporary pacemaker, ECMO, or VAD as appropriate. • Initiate treatment with 1–2 mg/kg/day IV methylprednisolone or equivalent and convert to 1–2 mg/kg/day oral prednisone or equivalent upon improvement. • If event does not improve within 48 hours after initiating corticosteroids, consider adding an immunosuppressive agent. • If event resolves to Grade 1 or better, taper corticosteroids over ≥ 1 month.

Table 11 Guidelines for Management of Non-Hematologic Toxicities (cont.)

Event		Action to Be Taken
Immune-mediated myocarditis (cont.)	Grade 2	
 Withhold study treatment. Refer patient to cardiologist. Initiate treatment as per institutional guidelines and consider antiarrhythmic drugs, temporary pacemaker, ECMO, or VAD as appropriate. Consider treatment with 1–2 mg/kg/day IV methylprednisolone or equivalent and convert to 1–2 mg/kg/day oral prednisone or equivalent upon improvement. If event resolves to Grade 1 or better, resume study treatment. If corticosteroids have been initiated, they must be tapered over ≥ 1 month to ≤ 10 mg/day oral prednisone or equivalent before atezolizumab can be resumed. Contact Medical Monitor before resuming atezolizumab. If event does not resolve to Grade 1 or better while withholding atezolizumab, permanently discontinue atezolizumab and contact Medical Monitor.
	Grade 1	
 Refer patient to cardiologist. Initiate treatment as per institutional guidelines.
Venous thrombosis or embolism		
 Withhold lenalidomide. Start anticoagulation treatment. After patient has been stabilized on anticoagulants and any complications of the thromboembolic event have been managed, lenalidomide may be resumed at current dose at investigator's discretion, dependent upon a benefit–risk assessment. Anticoagulants should be continued during the course of lenalidomide treatment.
Immune-mediated myositis	Grade 4	
 Permanently discontinue atezolizumab and contact Medical Monitor (refer to Appendix 10 for further guidance).
	Grade 3	
 Withhold atezolizumab for up to 12 weeks after event onset^d and contact Medical Monitor (refer to Appendix 10 for further guidance).
	Grade 2	
 Withhold atezolizumab for up to 12 weeks after event onset^d and contact Medical Monitor (refer to Appendix 10 for further guidance).
	Grade 1	
 Continue atezolizumab. Refer patient to rheumatologist or neurologist. Initiate treatment as per institutional guidelines.

Table 11 Guidelines for Management of Non-Hematologic Toxicities (cont.)

Event		Action to Be Taken
Suspected HLH or MAS		
 Permanently discontinue atezolizumab and contact Medical Monitor (refer to Appendix 10 for further guidance).
Other non-hematologic toxicities (i.e., not described above), excluding alopecia, nausea, and vomiting	Grade 3 or 4	
Grade 4 events
 
 Permanently discontinue study treatment. 
Grade 3 events
 
 Withhold study treatment. If there is improvement to Grade ≤ 1 or baseline, resume obinutuzumab and atezolizumab at full dose and, if the event is considered related to lenalidomide, resume lenalidomide at a reduced dose per guidelines in Section 5.1.5 for current and subsequent cycles; if the event is not related to lenalidomide, resume lenalidomide at current dose. For Grade 3 laboratory abnormalities that are isolated, asymptomatic and considered not clinically significant, study treatment may be either continued or delayed and resumed at the current dose, upon improvement to at least Grade 2 at the investigator's discretion and in agreement with the Medical Monitor.
	Grade 2	
 Withhold study treatment. If there is improvement to Grade ≤ 1 or baseline, resume obinutuzumab and atezolizumab at full dose and resume lenalidomide at current dose. For Grade 2 laboratory abnormalities that are isolated, asymptomatic and considered not clinically significant treatment may be continued at the current dose at the investigator's discretion.

CT= computed tomography; FL= follicular lymphoma; G-CSF=granulocyte colony-stimulating factor; HLH =hemophagocytic lymphohistiocytosis; IRR=infusion-related reaction; IV=intravenous; LMWH=low-molecular-weight heparin; MAS =macrophage activation syndrome; NCI CTCAE=National Cancer Institute Common Terminology Criteria for Adverse Events; NHL =non-Hodgkin's lymphoma; NSAID =nonsteroidal anti-inflammatory drug; TLS=tumor lysis syndrome; TSH=thyroid-stimulating hormone; ULN=upper limit normal.

^a Dose modifications apply only to events that are considered to be related to lenalidomide.

^b According to Cairo-Bishop classification system.

^c Graded according to NCI CTCAE Version 3.0.

^d Atezolizumab may be withheld for a longer period of time (i.e., > 12 weeks after event onset) to allow for corticosteroids (if initiated) to be reduced to the equivalent of ≤ 10 mg/day oral prednisone. The acceptable length of the extended period of time must be agreed upon by the investigator and the Medical Monitor.

^e If corticosteroids have been initiated, they must be tapered over ≥ 1 month to the equivalent of ≤ 10 mg/day oral prednisone before atezolizumab can be resumed.

^f Resumption of atezolizumab may be considered in patients who are deriving benefit and have fully recovered from the immune-mediated event. Patients can be re-challenged with atezolizumab only after approval has been documented by both the investigator (or an appropriate delegate) and the Medical Monitor.

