5.1.3.8 Renal Impairment

Lenalidomide is substantially excreted by the kidney. Patients with renal impairment (i.e., calculated creatinine clearance < 60 mL/min) will not be enrolled in this study. Renal function will be monitored during the study, and the lenalidomide dose may be adjusted as outlined in Section [5.1.5](#) (see [Table 10](#)).

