5.1.5 Management of Specific Adverse Events

Study treatment may be delayed for toxicity for a maximum amount of time, as specified in the tables below. If study treatment is delayed for longer than the specified maximum, study treatment will be permanently discontinued. Treatment delays apply to all toxicities described below; dose modifications apply only to toxicities that are considered

to be related to lenalidomide. There will be no dose reductions of obinutuzumab or atezolizumab.

The lenalidomide dose may be reduced in 5-mg increments one or two times, depending on the starting dose, as outlined in [Table 9](#). There will be no more than one dose reduction per treatment cycle. If the lenalidomide dose is reduced, re-escalation is not permitted.

Table 9 Lenalidomide Dose Reduction

Starting Dose	First Reduction	Second Reduction
20 mg	15 mg	10 mg
15 mg	10 mg	5 mg
10 mg	5 mg	—

If a lenalidomide-related toxicity occurs during lenalidomide treatment (i.e., before Day 21 of the cycle), lenalidomide must be withheld until criteria for recovery have been met (i.e., improves to Grade ≤ 2 or baseline values).

If recovery is observed prior or on Day 15 of the cycle, lenalidomide may be resumed at the same dose for the remainder of the cycle (through Day 21; missed doses will not be made up) at the discretion of the investigator. If the investigator considers that resuming lenalidomide at the same dose within the cycle represents an unacceptable risk for the patient, lenalidomide shall be resumed at reduced dose or withheld for the remainder of the cycle. For subsequent cycles, lenalidomide will be resumed at reduced doses.

If recovery is observed after Day 15 of the cycle, lenalidomide will not be resumed for the current cycle. For subsequent cycles, lenalidomide will be resumed at reduced doses.

Guidelines for management of toxicities during induction are provided in [Section 5.1.5.1](#). Guidelines for management of toxicities during maintenance are provided in [Section 5.1.5.2](#).

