
G-CSF = granulocyte colony-stimulating factor; LMWH = low-molecular-weight heparin.

^a Dose modifications apply only to events that are considered to be related to lenalidomide.

^b If cytopenia is thought to be caused mainly by non-Hodgkin's lymphoma infiltration of the bone marrow, the investigator may decide not to reduce the dose of lenalidomide.

^c For Grade 3 neutropenia, only if sustained (≥ 7 days) Grade 3 or \geq Grade 3 associated with fever (temperature $\geq 38.5^\circ\text{C}$).

Non-Hematologic Toxicities during Induction Treatment

[Table 11](#) provides guidelines for management of non-hematologic toxicities that occur during induction treatment.

Toxicities associated or possibly associated with atezolizumab treatment should be managed according to standard medical practice. Additional tests, such as autoimmune serology or biopsies, should be used to evaluate for a possible immunogenic etiology. For detailed information regarding management of adverse events associated with atezolizumab, please refer to the [Appendix 10](#).

Table 11 Guidelines for Management of Non-Hematologic Toxicities

Event	Action to Be Taken
General guidance for treatment delays and discontinuation	
 • If toxicity occurs before Cycle 1 Day 8 or Cycle 1 Day 15, these doses of obinutuzumab will not be skipped but given after resolution of toxicity. • When a treatment cycle is delayed because of a toxicity resulting from any component of the regimen, all study treatment should generally be held and resumed together to remain synchronized. • If it is anticipated that atezolizumab will be delayed by >21 days, obinutuzumab and lenalidomide should be given without atezolizumab if there is no contraindication. • If one drug is discontinued, treatment with the other two drugs may be continued for patients experiencing clinical benefit as determined by the investigator after discussion with the Medical Monitor. • Permanently discontinue study treatment if any of the following events occur: 
 – Grade ≥ 3 non-immune-mediated adverse event that is considered to be related to study treatment and does not resolve to Grade ≤ 2 within 21 days – Non-immune-mediated adverse event that is considered to be treatment related and requires study treatment to be withheld for >21 days – Immune-mediated adverse event that requires atezolizumab to be withheld for >42 days, unless approved by the Medical Monitor

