IRRs and anaphylaxis	
 • Guidelines for management of IRRs are provided in Sections 4.3.2.1 (obinutuzumab) and 4.3.2.2 (atezolizumab). • Metamizole (dipyrone) is prohibited in treating atezolizumab-associated IRRs because of its potential for causing agranulocytosis. • In case of anaphylaxis, study treatment should be permanently discontinued.
Renal toxicity	
 • Adjust the dose of lenalidomide^a as outlined below: 
 – If creatinine clearance is ≥ 30 but < 60 mL/min, lenalidomide should be given at a dose of 10 mg/day. – If creatinine clearance is < 30 mL/min and dialysis is not required, lenalidomide should be given at a dose of 10 mg every other day. – If creatinine clearance is < 30 mL/min and dialysis is required, lenalidomide should be given at a dose of 5 mg/day. On dialysis days, the dose should be administered after dialysis.

Table 11 Guidelines for Management of Non-Hematologic Toxicities (cont.)

	Event	Action to Be Taken
TLS	Clinical TLS ^b	
 • Withhold study treatment. • Correct electrolyte abnormalities, monitor renal function and fluid balance, and administer supportive care, including dialysis as indicated. Rasburicase therapy (if approved by the local health authority) may be administered as needed to reduce hyperuricemia. • If symptoms resolve completely, resume atezolizumab and obinutuzumab at full dose and resume lenalidomide at a reduced dose^a per guidelines in Section 5.1.5 for current and subsequent cycles. • Perform chemistry panel every other day for the first week after re-initiation of lenalidomide.
	Laboratory TLS ^b	
 • Withhold study treatment. • Correct electrolyte abnormalities, monitor renal function and fluid balance, and administer supportive care as clinically indicated. • If laboratory abnormalities have resolved completely, resume atezolizumab and obinutuzumab at full dose and resume lenalidomide either at current dose or at a reduced dose^a per guidelines in Section 5.1.5 for current and subsequent cycle, at the investigator's discretion.
Peripheral neuropathy	Grade 4 or Myasthenia gravis (any grade) or Guillain-Barre (any grade)	
 • Permanently discontinue study treatment. • Initiate treatment as per institutional guidelines.

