	Grade 2	
 • Withhold atezolizumab for up to 12 weeks after event onset.^d Contact Medical Monitor. • Refer patient to renal specialist. • Consider renal biopsy and supportive measures as indicated. • Corticosteroids and/or additional immunosuppressive agents should be administered as clinically indicated. • If event resolves to Grade 1 or better, resume atezolizumab.^e • If event does not resolve to Grade 1 or better while withholding atezolizumab, permanently discontinue atezolizumab and contact Medical Monitor.^f
	Grade 1	
 • Continue study treatment. • Monitor kidney function, including creatinine, closely until values resolve to within normal limits or to baseline values.

Table 11 Guidelines for Management of Non-Hematologic Toxicities (cont.)

AST, ALT, or bilirubin increase	Grade ≥ 3 (or $\geq 10 \times$ ULN for patients with liver involvement)	
 • Withhold study treatment and monitor liver enzymes at least every 7 days. • Investigate etiology. Consult with a hepatologist if immune etiology is suspected (refer to Appendix 10 for guidance in case of suspected immune-mediated hepatitis). • For immune-mediated hepatopathy: 
 - Treat with corticosteroids following guidance provided in the Appendix 10. - Permanently discontinue atezolizumab - Obinutuzumab may be resumed at full dose and lenalidomide at reduced dose for current and subsequent cycles as specified below, at investigator's discretion and after approval by the Medical Monitor. • If immune etiology is unlikely and there is improvement to Grade ≤ 1, resume obinutuzumab and atezolizumab at full dose and resume lenalidomide at a reduced dose^a per guidelines in Section 5.1.5 for current and subsequent cycles.
	Grade 2 lasting > 5–7 days	
 • Withhold atezolizumab. • If immune etiology is suspected, treat with corticosteroids according to guidance provided in the Appendix 10. • If there is improvement to Grade ≤ 1, resume atezolizumab after corticosteroids have been tapered (refer to Appendix 10 for guidance). Contact Medical Monitor before resuming atezolizumab.

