Immune-mediated nephritis has been associated with the administration of atezolizumab. Eligible patients must have adequate renal function. Renal function, including serum creatinine, should be monitored throughout study treatment. Patients with abnormal renal function should be evaluated and treated for other more common etiologies (including prerenal and postrenal causes, and concomitant medications such as non-steroidal anti-inflammatory drugs). Refer the patient to a renal specialist if clinically indicated. A renal biopsy may be required to enable a definitive diagnosis and appropriate treatment.

Management guidelines for nephritis are provided in Section [5.1.5.1 Table 11](#).

IMMUNE-MEDIATED MYOSITIS

Immune-mediated myositis has been associated with the administration of atezolizumab. Myositis or inflammatory myopathies are a group of disorders sharing the common feature of inflammatory muscle injury; dermatomyositis and polymyositis are among the most common disorders. Initial diagnosis is based on clinical (muscle weakness, muscle pain, skin rash in dermatomyositis), biochemical (serum creatine kinase increase), and imaging (electromyography/MRI) features, and is confirmed with a muscle biopsy.

Patients with signs and symptoms of myositis, in the absence of an identified alternate etiology, should be treated according to the guidelines in [Table 4](#).

Appendix 10
Risks Associated with Atezolizumab and Guidelines for
Management of Adverse Events Associated with Atezolizumab
(cont.)

Table 4 Management Guidelines for Immune-Mediated Myositis

Event	Management
Immune-mediated myositis, Grade 1	
 • Continue atezolizumab. • Refer patient to rheumatologist or neurologist. • Initiate treatment as per institutional guidelines.

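### Induction renal dose bands for lenalidomide apply only when the renal decline is attributed to lenalidomide, so other declines with no hold or stop rule get no dose adjustment

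*Combined protocol and SAP*

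**What the plan says.** The renal toxicity row of Table 11 opens with "Adjust the dose of lenalidomide^a as outlined below" and then gives three bands:

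- clearance 30 to below 60 mL/min: 10 mg daily
- clearance below 30 mL/min without dialysis: 10 mg every other day
- clearance below 30 mL/min with dialysis: 5 mg daily

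Footnote a to Table 11 reads "Dose modifications apply only to events that are considered to be related to lenalidomide". Section 5.1.5 carries the same restriction in its body text: "Treatment delays apply to all toxicities described below; dose modifications apply only to toxicities that are considered" related to that drug.

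Section 5.1.3.8 gives the reason for renal dosing, which is substantial renal excretion of lenalidomide. It continues: "Renal function will be monitored during the study, and the lenalidomide dose may be adjusted as outlined in Section" 5.1.5. The table it points to is Table 10, which covers hematologic toxicities.

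**The concern.** A relatedness test suits a reduction made because the drug is causing harm. It does not suit an adjustment made because the drug is being cleared more slowly. If lenalidomide leaves the body through the kidney, exposure rises when clearance falls, whatever lowered it. The marker and the Section 5.1.5 sentence therefore switch off the adjustment in cases where its stated rationale still applies.

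The protocol expects such cases. Under Renal Events, Appendix 10 tells investigators to look for "other more common etiologies (including prerenal and postrenal causes, and concomitant medications such as non-steroidal anti-inflammatory drugs". Section 4.5.6 specifies CT with intravenous contrast. The Grade 1–2 tumor flare row of Table 11 continues study treatment and allows NSAIDs. Because Section 4.1.2 excludes only clearance below 60 mL/min, a patient can enter at 60 and cross the first band after a small fall.

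Patient safety in induction is at stake. Section 5.1.3.2 warns of significant neutropenia and thrombocytopenia with lenalidomide. Sections 1.4.3.2 and 3.3.2.2 report that more Grade 3 or 4 neutropenia at 25 mg is what set 20 mg as the recommended dose with obinutuzumab. A site that follows the footnote keeps the patient on 15 or 20 mg; a site that follows clearance gives 10 mg or less.

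**Working it through.** There is no sample size, power or error rate to reproduce. The check has a textual part and a dose comparison.

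**1. Is the limit lifted anywhere?** Section 5.1.3.8 names no cause, but its verb is permissive and it sends the reader to Section 5.1.5, where the limit sits. No other text applies the clearance bands regardless of cause.

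**2. Does another rule catch a decline not attributed to lenalidomide?**

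| Rule | Effect on lenalidomide |
|---|---|
| Tumor lysis syndrome rows, Table 11 | Withheld; outside the claim |
| Immune-mediated nephritis, Grade 3–4 | Stopped; outside the claim |
| Immune-mediated nephritis, Grade 2 | Row names only atezolizumab: "Withhold atezolizumab for up to 12 weeks after event onset" |
| Immune-mediated nephritis, Grade 1 | Study treatment continues |
| General guidance, long atezolizumab delay (over 21 days) | "obinutuzumab and lenalidomide should be given without atezolizumab if there is no contraindication"; no renal dose given |
| Mid-cycle withholding, Section 5.1.5 | Lenalidomide-related toxicity only |
| 21-day stop rules, Section 4.6.2 | Require relatedness to study treatment |
| Catch-all row | "Other non-hematologic toxicities (i.e., not described above), excluding alopecia, nausea, and vomiting"; renal toxicity has its own row |

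In the Grade 2 case, the general advice to hold and restart all drugs together may pause lenalidomide. However, a hold of up to 12 weeks (84 days) can exceed the 21-day point at which lenalidomide is to go on without atezolizumab.

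What remains is Grade 1 and Grade 2 nephritis, and declines from contrast, dehydration or concomitant drugs.

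**3. How large is the excess?** Inputs are the induction doses in Section 4.3.2.3 (15 or 20 mg, with possible de-escalation to 10 mg), given on Days 1–21, and the Table 11 bands. The ratio is the unadjusted dose per cycle divided by the band dose per cycle.

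- Unadjusted: 20 × 21 = 420 mg; 15 × 21 = 315 mg; 10 × 21 = 210 mg.
- Band 30 to below 60: 10 × 21 = 210 mg.
- Band below 30, no dialysis: every other day from Day 1 to Day 21 is 11 doses, so 11 × 10 = 110 mg.

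| Current dose | 30 to <60 mL/min | <30 mL/min, no dialysis |
|---|---|---|
| 20 mg | 420/210 = 2.0 | 420/110 = 3.8 |
| 15 mg | 315/210 = 1.5 | 315/110 = 2.9 |
| 10 mg | 210/210 = 1.0 | 210/110 = 1.9 |

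Taking every-other-day dosing as a mean of 5 mg per day gives 4, 3 and 2 in the last column. The dialysis band (5 mg daily) gives the same 4, 3 and 2. Maintenance lenalidomide is 10 mg, so the first band brings no excess there.

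**4. Would the decline be seen?** Yes. The chemistry panel includes calculated creatinine clearance (Section 4.5.7). Appendix 1, with its footnote restricting Days 8 and 22 to Cycles 2 and 3, gives 4 panels in Cycle 1, 4 in each of Cycles 2–3 and 2 in each of Cycles 4–6: 4 + 8 + 6 = 18. The decline would be detected; what is missing is a dose instruction.

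**5. How many patients?** The documents give no frequency. If 2% to 10% of the 46 planned patients were affected, that would be 46 × 0.02 = 0.9 to 46 × 0.10 = 4.6, or about 1 to 5. That range is an assumption, and the true number could be zero.

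**The case against.** The best reply is that this is a misplaced marker. The relatedness sentence in Section 5.1.5 sits beside the Table 9 scheme of 5-mg steps, whereas the renal row sets absolute doses by clearance, takes 20 mg straight to 10 mg, and uses an every-other-day regimen that is not a Table 9 level. Marker placement is uneven elsewhere in Table 11: footnote a is attached to a hold in the progressive multifocal leukoencephalopathy row and is absent from the reduced dose in the Grade 3–4 tumor flare row. That is a fair account of what the sponsor probably intended. It does not change the rule, because Section 5.1.5 states the limit in its own text.

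It can also be argued that if footnote a removes unrelated declines from the renal row, they fall into the catch-all row, which would withhold treatment from Grade 2. But the footnote narrows the action, not the subject: renal toxicity is still described above the catch-all. That row also works by grade rather than clearance and does not reach Grade 1.

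Other mitigations are real but partial:

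- Section 4.5.6 allows MRI or non-contrast CT when renal clearance is impaired. That protects patients already impaired, not those in whom contrast causes the first fall.
- The Grade 2 nephritis row asks for Medical Monitor contact and renal referral.
- The rule for long atezolizumab delays has a contraindication clause.
- An investigator may withdraw a patient on safety grounds.

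All of these rely on judgment to override a written limit.

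Three points stand. Nothing in the documents shows that Grade 1 nephritis would take clearance below 60 mL/min. The 1-to-5-patient figure carries little weight. Lymphoma-related impairment admitted under the exception in Section 4.1.2 is a baseline condition, not a decline during induction, and is a separate eligibility matter.

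**Conclusion.** The concern holds. As written, the induction rule denies the renal adjustment to a patient whose decline is not attributed to lenalidomide and to whom no hold or stop rule applies. The figure to carry forward is 1.5 to 2.0 times the table's dose at 30 to 59 mL/min. The 2.9 and 3.8 ratios below 30 mL/min hold only if nothing else has stopped or held treatment.

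This rests on reading footnote a and Section 5.1.5 literally. Many investigators would dose by clearance anyway or ask the Medical Monitor, and the number affected is unknown. It should be corrected because it gives an unsafe instruction for a renally cleared drug and lets sites reach different doses from one row.

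**What to change.** 1. Remove the footnote a marker from the renal toxicity row of Table 11.
2. Add one sentence to Section 5.1.5: the creatinine clearance bands in Table 11 apply whatever the cause of the renal impairment, as an exception to the relatedness limit.

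Two related items can go in the same amendment, though the point does not depend on them. The clearance criterion in Section 4.1.2 allows an exception for lymphoma, while Section 5.1.3.8 says such patients will not be enrolled; the two should agree. The pointer in Section 5.1.3.8 should be to Table 11, not Table 10.

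The cost is wording only. Clearance is already in every chemistry panel, and Section 4.3.1.3 already supplies 5- and 10-mg capsules.
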